#### 8.2 Statistical analysis

8.2.1 Summary of baseline data and flow of participants

The flow of participants through the study with outcome of the index tests (stool FIT and urine VOC) will be produced. The diagram will follow the template from STARD (Standards for Reporting of Diagnostic Accuracy Studies)(39). Descriptive statistics for the population will be presented in tables with comparisons made between those who do and do not consent to participate, and those who do and do not fully participate by providing a complete set of samples. Full details will be given for exclusions from analysis with reasons where available.

IRAS 282247\_RECEDE protocol\_v2.2\_11.02.2022 Page 27 of 50

Demographics and baseline characteristics will be summarised as mean and standard deviation, median and interquartile range (for continuous outcome) or frequency and percentage (for categorical outcome). The final diagnosis including histology where available from colonoscopy (the reference test) specifically diagnosis of SBD will be summarised as frequency and percentage.

#### 8.2.2 Primary outcome analysis

The primary outcome is diagnostic accuracy - sensitivity, specificity, NPV and PPV of the dual index test, FIT and VOC. A FIT result that is >10 µgHb/g faeces OR a VOC result with predicted probability >0.63 implies that the participant is defined as having SBD and need to be referred for colonoscopy. We will report 2x2 tables of test accuracy of the dual test by the reference standard (final report from the CTC or colonoscopy examination and confirmatory histology report of SBD which is either colon cancer, colorectal adenomas or inflammatory bowel disease), alongside summary measures of sensitivity, specificity, NPV and PPV, and their 95% confidence intervals. Confidence intervals for sensitivity and specificity estimates that are very close to 1.0 will be according to the Zhou-Li method and the intervals for NPV and PPV estimates that are very close to 1.0 will be according to the Bayesian method (38). These test accuracy estimates will be used in the economic model.

We will analyse the combined FIT+VOC test results as both parallel (results from both tests are interpreted in combination) and serial testing (VOC performed only if FIT negative, i.e. <10  $\mu$ gHb/g faeces). The "or" rule will be considered in the interpretation of both parallel and serial tests where the diagnosis is positive when either test is positive (FIT >10  $\mu$ gHb/g faeces and/or VOC predicted probability >0.63), and negative when both are negative (FIT <10  $\mu$ gHb/g faeces and VOC predicted probability <0.63). In the serial test, if the FIT is positive (FIT >10  $\mu$ gHb/g faeces) then the diagnosis is positive. Otherwise, use the result from VOC and if it is positive (VOC predicted probability >0.63) then the diagnosis is positive. If the VOC result is also negative then the diagnosis is negative. Mathematically, both methods would give the same diagnostic results but would make a difference in the economic model.

A 2x2 table of test accuracy for each individual index test by the reference test will also be presented. Sensitivity, specificity, PPV and NPV will also be presented with their 95% confidence intervals for FIT only and VOC only. Participants with missing data for either of the index tests (FIT or VOC) or the reference standard (colonoscopy) will be excluded from this analysis.

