#### Secondary outcome

Secondary outcome measures will include:

- I. ROC curve of stool FIT plus urine VOC in detection of SBD.
- II. The potential number of colonoscopies and CTCs avoided in those without SBD,
- III. Total NHS & Personal Social Services (PSS) costs, and
- IV. Total quality-adjusted life years (QALYs) associated with each option.

Exploratory outcome measures will include:

Calculation of the number of CTC negative participants who later present with SBD or microscopic colitis

IRAS 282247\_RECEDE protocol\_v2.2\_11.02.2022 Page **13** of **50** 

 Sensitivity, specificity, NPV and PPV of stool FIT plus urine VOC in the detection of SBD + microscopic colitis

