#### 6.6 Follow Up

Participants referred to CTC will be followed up for a longer duration, at least 52 weeks post-CTC procedure or until the study results are un-blinded. The follow-up check is on the participant's medical records to determine if they have a lower GI diagnosis later on that was not picked up by CTC.

IRAS 282247\_RECEDE protocol\_v2.2\_11.02.2022 Page **22** of **50** 

It is anticipated that a small number of participants may return false negative results from their CTC as CTC is not able to pick up microscopic colitis, a treatable serious bowel condition. Whereas it is predicted that dual testing FIT + VOC may be able to detect if microscopic colitis is present in this population. Therefore those who return a negative CTC, but following analysis show a FIT or VOC positive result and did not have any further specialist lower GI care following checks on their medical records, will be re-contacted and recommended for further investigation with colonoscopy. The prevalence of microscopic colitis in those referred for further bowel investigation is small (<0.5%) and so we predict that this will only occur in a small number of participants.

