#### 7.5 Reference test

The reference test is the final report from the CTC or colonoscopy examination and confirmatory histology report. Biopsies are required as per national guidance (4) in the investigation of participants with lower gastrointestinal symptoms even in the absence of macroscopic abnormalities.

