We will investigate the types of SBD and microscopic colitis, and the number of cases missed by CTC, FIT and VOC analyses. Depending on the number of microscopic colitis cases, we may explore the accuracy of FIT and VOC in detecting microscopic colitis with the other SBDs.

A full statistical analysis plan will be written and signed off prior to conducting the final analyses.

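### SBD confirmed in the planned records check after a negative CTC stays 'no SBD' in the primary 2x2 table, and no stated analysis shows the effect on sensitivity and NPV

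*Protocol*

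**What the plan says.** Section 7.5 defines the reference: "The reference test is the final report from the CTC or colonoscopy examination and confirmatory histology report". Section 8.2.2 uses the same definition for the primary table, the "final report from the CTC or colonoscopy examination and confirmatory histology report of SBD", and section 8.2.3 repeats it for the threshold work. Clinical follow-up appears in none of them. Table 1 collects the CTC or colonoscopy result at 3 weeks and puts follow-up of CTC-negative patients in a separate, later column.

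Section 6.6 follows CTC participants for longer, "at least 52 weeks post-CTC procedure or until the study results are un-blinded", through their medical records, to "determine if they have a lower GI diagnosis later on that was not picked up by CTC". It also provides that CTC-negative participants who are FIT or VOC positive, and have had no further specialist lower GI care, are re-contacted with a recommendation for further investigation.

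The protocol names two uses for the later diagnoses. Section 1.2 lists an exploratory outcome: "Calculation of the number of CTC negative participants who later present with SBD or microscopic colitis". The end of section 8.2.3 will look at "the number of cases missed by CTC, FIT and VOC analyses". Neither leads back to the 2x2 table.

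**The concern.** One participant can be SBD in the exploratory count and 'no SBD' in the primary table. The resulting error depends on the dual test:

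- **Dual-positive:** the participant is scored as a false positive although the test was right. Specificity and PPV are slightly too low.
- **Dual-negative:** the participant is scored as a true negative although the test missed disease. Sensitivity and NPV are too high.

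The second error matters more. Section 8.1 bases the sample size on sensitivity because the strategy must not miss disease, and it also stresses NPV. The same reference drives the choice of thresholds at 97% sensitivity (8.2.3), and the accuracy estimates feed the economic model (8.2.2, 8.3).

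The two reference procedures may also differ in what they detect. Section 1.6 supports CTC by its sensitivity for colorectal cancer and large polyps. SBD in the study summary also includes inflammatory bowel disease and adenomas with high-grade dysplasia.

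**Working it through.** **1. The plan's own figures (section 8.1).** Inputs: 200 SBD cases, prevalence 19%, 55% returning both samples, sensitivity 0.97, CI width 0.05.

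- 200 / 0.19 = 1,052.6, so 1,053 evaluable participants.
- 1,053 / 0.55 = 1,914.5, so 1,915 recruited.
- 0.97 x 200 = 194 true positives and 6 false negatives.
- The Wilson interval for 194/200 is 0.936 to 0.986, width 0.050. (The Zhou-Li equations are not legible in the text at hand, so a standard interval was used.)

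These agree with the protocol. Nothing below changes the sample size.

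**2. Effect per reclassified case.** Let k be the number of CTC-negative participants with SBD confirmed in the records check.

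- All k dual-negative: sensitivity = 194 / (200 + k).
- All k dual-positive: sensitivity = (194 + k) / (200 + k).

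| k | all dual-negative | all dual-positive |
|---|---|---|
| 0 | 0.970 | 0.970 |
| 1 | 0.965 | 0.970 |
| 3 | 0.956 | 0.970 |
| 6 | 0.942 | 0.971 |
| 9 | 0.928 | 0.971 |

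With six dual-negative cases the Wilson interval is 0.901 to 0.966, so its upper limit is below 0.97. With six cases split evenly, sensitivity is 197/206 = 0.956.

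**3. NPV, PPV and specificity.** These need the number of dual-negatives, which the protocol does not predict. Figure 6 in section 8.1 considers 400 to 600 in 1,000. Assume 500 of 1,053, so 494 true negatives, 553 dual-positives and 853 without SBD.

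- NPV = (494 - k) / 500 if all k are dual-negative: 0.988 at k = 0, 0.982 at k = 3, 0.976 at k = 6. Each case costs 1/500 = 0.2 points.
- If six cases are all dual-positive, PPV goes from 194/553 = 0.351 to 200/553 = 0.362, and specificity from 494/853 = 0.579 to 494/847 = 0.583.

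**4. How large k might be.** The protocol gives no CTC miss rate and no planned CTC share. Section 1.6 reports that over 25% of referrals have CT scans, which includes regular CT, so 25% is only a proxy. With miss rate m and equal SBD prevalence across modalities, k = 200 x share x m / (1 - m), if every missed case later appears in the records.

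- Share 25%, m assumed at 2%, 5%, 10%, 15%: k = 1.0, 2.6, 5.6, 8.8, or about 1, 3, 6, 9.
- Share 50%, m assumed at 10%: k = 11.1, or about 11.

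Only cases that reach the records can be reclassified, so these are upper figures for each assumed m.

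**5. Mixed results.** If the dual test detects a fraction s of these cases, sensitivity = (194 + k x s) / (200 + k).

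- s = 0.97: 0.970 for any k.
- s = 0.85 (the FIT-alone sensitivity for inflammatory bowel disease in section 8.1): (194 + 5.1) / 206 = 0.967 at k = 6, and (194 + 7.65) / 209 = 0.965 at k = 9.
- s = 0: the dual-negative column above.

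**The case against.** **A reader might infer that section 6.6 itself declares SBD to have been missed by CTC.** It does not. It speaks of a lower GI diagnosis, and its only named example is microscopic colitis, which is outside the SBD definition. SBD enters through the exploratory outcome in 1.2 and the end of 8.2.3. Nor is a later presentation proof of disease at the time of CTC, since after a year or more some cases may be new. A procedure report as reference, with later presentations reported separately, is a defensible choice. This stands.

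**A reader might also infer that the composite should replace the primary reference.** The case against is strong. FIT is used to triage timing, a triage FIT within 4 weeks of the procedure can serve as the index test (1.6), and triage results sit in patient records (7.3). A FIT-positive, CTC-negative patient is plausibly more likely to be investigated again in routine care, which would add cases mainly among index positives and push sensitivity up. The extended follow-up also covers CTC participants only. Hence a sensitivity analysis, not a new primary.

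**The large shifts are extremes.** They need every reclassified case to be dual-negative. In the illustrative table 58% of participants without SBD are dual-negative. Even an uninformative test would leave six of six negative with probability about 0.58^6, or 4%. This stands.

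**The data are not used only for a count.** Section 1.2 also lists dual-test accuracy for SBD plus microscopic colitis, and CTC participants could contribute microscopic colitis only through later findings. But the protocol does not say that this analysis uses the records check, and it would not isolate SBD.

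**An SAP is promised (8.2.3) and may hold such an analysis.** That is possible. The point here is what the protocol fixes: a reference without follow-up, and exploratory use of the later diagnoses.

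**Biopsy.** Section 7.5 calls for biopsies "even in the absence of macroscopic abnormalities", and a CTC alone yields none. That is a separate matter, because the records check supplies no tissue for participants who are not investigated again.

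**Conclusion.** The point holds in a limited form. As defined, the primary table keeps a CTC-negative participant with later confirmed SBD as 'no SBD', and no analysis stated in the protocol shows what follows for SBD alone. The direction is clear for dual-negative cases: sensitivity falls by about 0.5 points per case once they are reclassified, and NPV by about 0.2 points under the assumed 500 dual-negatives. Dual-positive cases barely move sensitivity.

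The total is not known. It depends on the CTC share, the CTC miss rate, the fraction of missed cases that reach the records, and how the dual test performs in them. The documents give none of these for this study. The plausible result runs from no change to a drop of a few points, the latter only in unfavourable scenarios. The documents do not support a claim that the primary sensitivity is overstated by any particular amount. They do support showing whether a result near 0.97 survives this misclassification, using data the study already plans to collect.

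**What to change.** Keep the report-based reference as primary. Add to section 8.2.2 (or confirm that the SAP contains):

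1. A pre-specified sensitivity analysis in which a CTC-negative participant with SBD confirmed in the 6.6 records check, within a fixed window such as 52 weeks, counts as reference-positive. Apply the check alike to all CTC-negatives, whatever their FIT or VOC result, and adjudicate blind to both tests.
2. Exclusion from that analysis of diagnoses made only through the study's own recommendation to FIT- or VOC-positive participants. These could add cases among index positives only and would inflate sensitivity.
3. The 2x2 table shown separately for CTC and colonoscopy as reference.

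The cost is wording, one coded variable and a blinded adjudication step, since the follow-up data are already planned. State the downsides with the analysis: some cases may be new disease, a triage FIT known to clinicians may make records-based detection more likely in FIT-positives, and the analysis must wait for the records check.

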#### **STUDY SUMMARY**

	Objectives Outcome Measures
Planned study period	40 months
Sample size	1915
Study arms	All participants will receive the index tests: stool FIT and urine VOCs; and reference standard: full colonoscopy examination or CTC.
	Stool FIT and urine VOC
Reference standard Index tests	Final report from the CTC or colonoscopy examination and confirmatory histology report Stool FIT alone
Study participants	Participants referred from primary care to NHS Trusts that undertake colonoscopy or CTC will be approached to participate.
Study design	Multicentre – Prospective Diagnostic Accuracy Study
	*Significant Bowel Disease (SBD) is defined as those with colorectal cancer, significant pre-malignant polyps (adenomas with size >10mm or with high grade dysplasia)or inflammatory bowel disease
	If stool FIT plus urine VOC is sufficiently accurate it will enable a reduction in the number of colonoscopies and Computed Tomography Colonography (CTC) in those without SBD.
Study aim	To investigate the diagnostic accuracy of stool FIT plus urine VOC compared to stool FIT alone for detection of SBD*.
Research question	Can the addition of urine VOC to stool FIT testing rule out significant bowel disease (SBD) and by so doing, reduce unnecessary invasive tests (colonoscopy/CTC) – the right test for the right participant?
Study title	Reducing Colonoscopies in patients without significant bowEl DiseasE - RECEDE study

Primary	Diagnostic accuracy of stool FIT plus urine VOC compared to stool FIT alone to improve detection of SBD.	Sensitivity, specificity, negative predictive value (NPV) and positive predictive value (PPV) of stool FIT plus
		urine VOC in detection of SBD, using CTC or colonoscopy histology findings.
Secondary	Diagnostic accuracy of stool FIT plus urine VOC in detection of SBD	Receiver operating characteristic (ROC) curve of stool FIT plus urine VOC in detection of SBD.
	Impact on number of colonoscopies and CTCs undertaken	Calculation of potential number of colonoscopies and CTCs avoided in those without SBD.
	Cost effectiveness and colonoscopy/CTC disutility	Cost calculation, Quality of life (EQ-5D-5L) and quality adjusted life years (QALY) associated with utility of each diagnostic strategy (stool FIT and urine VOC)

Key Words:

FIT, urine VOC, diagnostic, colorectal cancer, adenoma, IBD, colonoscopy

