#### 1.2 Scientific Abstract

*Research Question*: Can the addition of urine VOC to stool FIT testing rule out significant bowel disease (SBD) and by so doing, reduce unnecessary invasive tests (colonoscopy/CTC) – the right test for the right participant?

*Background:* There is currently disparity between demand and available resources for colonoscopy. At present around 300,000 participants (and rising) are being referred annually to NHS trusts suspected of colorectal cancer (CRC) (1). These participants are offered invasive colonic examinations (colonoscopy or CT colonography) but only 30% will have significant bowel disease (2). Significant bowel disease (SBD) includes neoplasia (cancer and benign tumours) and significant treatable benign conditions such as inflammatory bowel disease (3). Of the remaining 70%, 40% have completely normal colonic investigations (2) and 30% have functional bowel conditions such as irritable bowel syndrome or diverticular disease.

Set against this there is and will remain for the foreseeable future a capacity shortfall for colonoscopy and CTC. This limits the ability of the NHS to extend colorectal cancer detection within the Bowel Cancer Screening Programme (BCSP) or to target those participants that present for the first time through the Emergency Department (25% of all colorectal cancer diagnoses).

The increasing demand, limited capacity and lack of a triage tests have left NHS trusts with a conundrum of how best to stratify those with symptoms and at risk of SBD including CRC. The National Institute for Health and Care Excellence (NICE) has recommended a stool test (faecal immunochemical testing for haemoglobin, known as FIT) in the assessment of those suspected of CRC (4). NICE have recommended 10  $\mu$ gHb/g faeces as the cut off for investigation of people with low risk symptoms who, account for only 10% of those referred with suspected CRC. When applied to high risk symptom groups, FIT will *miss* a significant number of participants with CRC (~10%) if used on its own at the threshold recommended by NICE (10  $\mu$ gHb/g faeces). FIT will also *miss* a large number of significant potentially pre-cancerous polyps (~40%) (6, 7). Early detection and removal of such polyps will reduce risk of CRC (8).

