#### 7.3 Stool FIT

Samples with traces of haemoglobin in the faeces at and above the cut off value  $10\mu$ gHb/g are defined as suspected SBD. Any previous FIT results collected to triage patients can be sourced from patient records.

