The urinary volatiles will be analysed in Manchester using "electronic nose" techniques using an array of gas sensors coupled with an appropriate polymeric pre-concentrator. Appendix 3 provides a detailed description of the technique being utilised at Manchester for VOC analysis. This technique provides multivariate data documenting differences in the chemical composition of the urinary volatiles that may contain volatile biomarkers for a condition. This allows screening of populations rapidly using chemometric data analysis, neural networks and receiver operator curves to distinguish one population from another, with receiver operating curves being used to measure the appropriate thresholds to be set to distinguish samples as having colon cancer, colorectal adenomas, inflammatory bowel disease or microscopic colitis. Unlike GCMS – this technique does not provide identities of individual biomarkers but considers the data derived from the entire complex mixture of volatile chemicals that are present in urine headspace.

A receiver characteristic curve (ROC) with an area under the curve (AUC) of 0.63 or greater will be applied for the detection of SBD (colon cancer, colorectal adenomas or, inflammatory bowel disease). The threshold for participants samples being defined as having SBD will be >0.63 (see Appendix D).

To determine the relationship to the stool test (which is a quantitative continuous variable) a canonical correlation test will be applied. The canonical correlation tool is often used in a multivariate analysis of correlation. Canonical is the statistical term for analysing latent variables (which are not directly observed) that represent multiple variables (which are directly observed). Canonical correlation analysis is the analysis of multiple-X multiple-Y correlation. The canonical correlation coefficient measures the strength of association between two canonical variates. Canonical correlation analysis is preferable in analysing the strength of association between two constructs. This is because it creates an internal structure containing different importance of single item scores that make up the overall score.

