#### 8.2.3 Secondary outcome analysis

To find the optimal threshold of FIT and VOC we will first plot the receiver operating characteristic (ROC) curves of both tests individually. The individual optimal threshold is the one that gives the greatest specificity whilst achieving the required 97% sensitivity to avoid colonoscopy or CTC. Secondly, we will plot combinations of the two tests in the ROC space and similarly, choose the combination of thresholds which has greatest specificity whilst achieving the required 97% sensitivity to avoid colonoscopy or CTC. The combined thresholds of FIT and VOC in the ROC space is done by combining every unit of FIT (from 7 to 120 µgHb/g faeces) with every unit of the predicted probability of VOC (from 0.63 to 1). Both the "or" and "and" rules will be used in combining the FIT and VOC results to define a case as positive (having SBD and requires colonoscopy) and negative (no SBD and does not require colonoscopy or CTC). The "or" rule is as described in Section 8.2.2. The "and" rule is when both FIT and VOC tests define a case as positive then the diagnosis is positive. If both tests are in discordant, i.e. only one of them defines a case as positive and the other defines it as negative then the diagnosis is negative. For each of the thresholds that we derive from the ROC curves, we will also report the NPV estimates. This will produce an overestimate of test accuracy, which we will use as a sensitivity analysis in the economic model, as a

more optimistic assumption to demonstrate the range of uncertainty. Similarly, the reference standard is the final report from the CTC or colonoscopy examination and confirmatory histology report of SBD.

Other secondary analyses include sensitivity, specificity, PPV and NPV estimates and their corresponding 95% CI for each individual condition of SBD (colorectal cancer, colorectal adenomasand inflammatory bowel disease) by each individual test and combination rules.

We will also estimate the compliance rates – return of stool and urine samples – by presence of SBD or not and individual conditions comprising SBD, as well as if samples are missing at random or not. All accuracy tests will be adjusted by covariates (demographics and/or clinical parameters) if there is an association between each covariate and the test results.

Appropriate procedures to account for the type of missing data will be performed for sensitivity analyses.

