The first two parts of the model will be run for each of the conditions classified as SBD (i.e. colorectal cancer, colorectal adenomas and inflammatory bowel disease).

Calculations will consider all key costs and consequences, including the costs and 'disutility' associated with having a colonoscopy or CTC. Model input will be drawn from relevant sources, including the RECEDE study and the available literature. For example, parameters related to the diagnostic characteristics of the compared options—which will be a key input in the first part of the model and a crucial parameter for the overall analysis—will be collected directly from RECEDE (we will model the accuracy at the thresholds pre-specified in the primary outcome, and the optimal thresholds from the exploratory analysis). Further information for the economic model, such as estimates of the rate of adverse outcomes associated with colonoscopies (e.g. bowel perforation and bleeding) or CTCs, preference-based health-related quality of life (utility) values and primary and secondary care resource use for the diagnostic part of the model will be collected from a sample of 370 RECEDE participants (20% of the total intended sample) recruited at UHCW. The questionnaires will continue to be administered until 370 participants have completed all five of their questionnaires.

In planning the study, we considered carefully whether collecting information on the 'disutility' of colonoscopy from patients at one site would introduce any unanticipated bias. We believe that the nature of the data we are interested in (impact of colonoscopy or CTC on patient's quality of life over the short time period before and after the procedure) and the fact that colonoscopy and CTC procedures and the preparation stage preceding them is well defined and standardised across NHS settings, makes it unlikely that single site data collection will results in any unanticipated bias or unrepresentativeness. Given this, and the fact that other sites indicated that further data collection (quality of life questionnaires) might be a barrier to recruitment, we felt that collecting data from a single site is sensible and justifiable.

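### The Study Summary limits SBD adenomas to those >10 mm or with high-grade dysplasia, but the primary 2x2 table in 8.2.2 lists colorectal adenomas with no limit

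*Protocol*

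**What the plan says.** **Target condition.** The Study Summary is the only place that gives a size or grade criterion. Besides colorectal cancer, it counts "significant pre-malignant polyps (adenomas with size >10mm or with high grade dysplasia)or inflammatory bowel disease".

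Four later sections drop the criterion:
- 8.2.2, the primary 2x2 table: "confirmatory histology report of SBD which is either colon cancer, colorectal adenomas or inflammatory bowel disease".
- 8.2.3, the secondary analyses: accuracy "for each individual condition of SBD (colorectal cancer, colorectal adenomasand inflammatory bowel disease").
- 7.4, the VOC test: "detection of SBD (colon cancer, colorectal adenomas or, inflammatory bowel disease").
- 8.3, the economic model: "i.e. colorectal cancer, colorectal adenomas and inflammatory bowel disease".

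Section 1.2 is looser again: "Significant bowel disease (SBD) includes neoplasia (cancer and benign tumours"). Appendix D reports VOC accuracy separately for high-risk adenoma and for all adenomas.

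**Index-test boundary.** Section 7.3 treats as suspected SBD "Samples with traces of haemoglobin in the faeces at and above the cut off value" of 10 µgHb/g. Section 8.2.2 calls FIT positive when >10, "and negative when both are negative (FIT <10" and VOC <0.63). VOC is positive when >0.63.

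**The concern.** The reference standard decides the columns of the primary table. A participant whose only finding is a small low-grade adenoma is a non-case under the Study Summary and a case under the literal wording of 8.2.2. All four primary accuracy measures depend on that label. So do the count of colonoscopies avoidable in people without SBD, the thresholds that 8.2.3 selects to reach 97% sensitivity, and the accuracy inputs to the economic model.

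The label may also affect the comparison with FIT alone. Section 1.9 names diminutive adenomatous polyps as a setting where FIT becomes less sensitive. It gives FIT sensitivity as 53% for adenomatous polyps, against 80% for cancer and 86% for inflammatory bowel disease (IBD). Counting small adenomas as disease would tend to lower the comparator's sensitivity.

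**Working it through.** **1. The plan's own sample size (8.1).** 200/0.19 = 1,052.6, rounded up to 1,053. Then 1,053/0.55 = 1,914.5, rounded up to 1,915. Both figures reproduce. At sensitivity 0.97 with 200 cases, the 95% interval width is 0.050 (Wilson), 0.047 (Wald) or 0.053 (Clopper-Pearson), in line with the stated 0.05. The Zhou-Li formula is not fully legible in the available text, so only these standard intervals were checked. Section 8.1 does not say which SBD definition the 19% uses.

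**2. How many people differ between the definitions.** Appendix D gives VOC sensitivity 0.93 (0.81 to 1.0) for high-risk adenoma and 0.91 (0.85 to 0.97) for all adenomas. If the intervals are Wald-type, n = p(1−p)/(h/1.96)², where h is the half-width. For the high-risk group h is taken from the lower limit, because the upper limit is cut at 1.0.
- High-risk: 0.93×0.07/(0.12/1.96)² = 17.
- All: 0.91×0.09/(0.06/1.96)² = 87.
- Difference: 87 − 17 = 70, and 70/562 = 12.5%.

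The published figures are rounded, so a range is needed.
- High-risk, moving p and h by 0.005 each: 0.935×0.065/(0.125/1.96)² = 14.9 and 0.925×0.075/(0.115/1.96)² = 20.2, so about 15 to 21.
- All, with h from 0.065 to 0.055: 74 to 104.
- Difference: 74 − 21 = 53 to 104 − 15 = 89.
- Scaled: 53/562×1,053 = 99 to 89/562×1,053 = 167, so roughly 100 to 167 of 1,053.

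This is a rounding range, not a confidence interval. Letting the all-adenoma estimate also move by 0.005 gives 71 to 109, and so about 50 to 94 people.

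*Check on the Wald assumption.* Applied to FIT sensitivity for cancer in Appendix D, 0.80 (0.66 to 0.93), the formula gives 0.80×0.20/(0.135/1.96)² = 34 cancers. Section 1.9 reports 7 cancers missed by FIT; at 80% sensitivity that implies 7/0.20 = 35.

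**3. Illustration of the effect on the primary estimates.** None of the following assumptions is a protocol figure for this purpose:
- 200 cases meet the Study Summary definition, with dual-test sensitivity 0.97 (194 positive, 6 negative).
- A further 105 participants (10%) have only small low-grade adenomas.
- The other 748 participants are adenoma-free non-cases with specificity 0.585 (438 negative, 310 positive).
- The dual test is positive in 50% or 91% of the 105. The 91% borrows the all-adenoma VOC figure from Appendix D, obtained at that study's own threshold.

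| | Study Summary label | 8.2.2 read literally |
|---|---|---|
| Cases | 200 | 305 |
| Sensitivity | 0.97 | 0.81 to 0.95 |
| Specificity | 0.52 to 0.57 | 0.585 |
| PPV | 0.32 to 0.35 | 0.44 to 0.48 |
| NPV | 0.99 | 0.88 to 0.97 |

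For example, literal sensitivity at 91% is (194 + 95.6)/305 = 0.95, and at 50% it is (194 + 52.5)/305 = 0.81.

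**4. FIT exactly 10.** Under 7.3 it is positive. Under the parallel rule in 8.2.2 it is neither positive nor negative. Under the stepwise serial rule, anything not >10 passes to VOC, so it is handled as not positive. With FIT = 10 and VOC negative, the serial rule gives a negative and the parallel rule gives no result, so the statement in 8.2.2 that both methods give the same results fails there. For FIT alone, each such SBD case moves sensitivity by 1/200 = 0.5 percentage points and each such non-case moves specificity by 1/853 = 0.12 points. The number of such results is unknown.

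**The case against.** **The short list may be shorthand.** Only the Study Summary says how SBD is defined. Sections 8.2.2 and 8.2.3 use the term SBD and then name its components, so an adenoma could be taken to enter the list only if it already qualifies as SBD. This reading is available. It is not secured: there is no cross-reference, the unrestricted wording appears in four sections, and Appendix D treats high-risk and all adenomas as different groups.

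**The size is soft.** This stands. The protocol never equates high-risk with >10 mm or high-grade dysplasia, and the Wald form is inferred. The published intervals are themselves not stable: the interval for FIT sensitivity of 0.80, from the same cited study, is 0.63 to 0.93 in section 1.9 and 0.66 to 0.93 in Appendix D. Some people with small adenomas may also be SBD through cancer or IBD. If the 19% already counted all adenomas, many of those who move lie inside the 200. With 91% positivity, sensitivity falls only from 0.97 to about 0.95, less than the planned interval width of 0.05; the larger fall needs an assumed 50%.

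**A reader might infer that the definition could be chosen after seeing results.** The document does not support this. Section 8.2.3 ends by requiring a full SAP to be signed off before the final analyses, and that SAP is not shown. What remains is that a SAP following the literal 8.2.2 would conflict with the Study Summary.

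**The boundary gap is minor.** This stands. The serial rule partly covers FIT = 10, and a VOC output of exactly 0.63 is one point on a 0-to-1 scale.

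**Conclusion.** The inconsistency holds as a matter of text, and it concerns who counts as diseased in the primary analysis. It should be corrected before unblinding. The number affected, about 53 to 89 of 562 or roughly 100 to 167 of 1,053, rests on three assumptions: that high-risk adenoma approximates the Study Summary criterion, that the intervals are Wald-type, and that the case mix is similar to the earlier study. The direction is clear: the literal wording adds reference-positives. The effect on sensitivity could be small or large, depending on how often the dual test is positive in small adenomas, which the protocol does not give.

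Two stronger inferences are not supported. The documents do not show that the VOC network has to be retrained on a single SBD label: section 7.4 and Appendix D describe assigning samples to separate disease classes. Nor do they show that results at exactly 10 or 0.63 would materially move the primary estimates.

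**What to change.** Before unblinding:

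1. Refer 7.4, 8.2.2, 8.2.3 and 8.3 to the explicit Study Summary definition of SBD, so that one definition applies throughout.
2. Report accuracy for any adenoma as a named secondary analysis.
3. State in 8.1 which definition the 19% prevalence and the 200 cases assume. If it is not the Study Summary definition, restate the expected number of cases or the precision.
4. Minor: reconcile 7.3 with 8.2.2 so that each test has one gap-free inequality for the analysis, covering FIT exactly 10 and VOC exactly 0.63.

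**Cost.** Items 1, 2 and 4 are changes of wording; section 7.7 already has the CTC, colonoscopy and histology reports collected. Item 3 may not be free. About 35 cancers plus 17 high-risk adenomas is 52/562 = 9.3%, or about 97 of 1,053, before any IBD. Reaching 19% would then need nearly 10% from IBD. If the restricted definition gives fewer than 200 cases, the interval widens: with 150 cases at sensitivity 0.97, the Wilson width is 0.059 instead of 0.050.
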